4.2 SCIENTIFIC RATIONALE FOR STUDY DESIGN

The ATT control group was selected to account for potential effects of intervention-related contacts (e.g., "attention") that are not specific to the PAS program components (e.g., the specific rehabilitation and exercise program being delivered in the PAS intervention). Additional comments regarding rationale for the study design are described in Section 4.1.

4.3 JUSTIFICATION FOR INTERVENTION

The intervention is described in detail in Section 6. The number, frequency and types of contacts were selected based on ability to deliver the PAS content, as well as feasibility of administration in real-world clinical settings. We chose for the first 2 PAS visits to be included within the context of routine post-TKA PT so that it would be integrated into routine care. The 4-week and 8-week contacts were selected to include a reasonable, feasible amount of contact – beyond the typical post-TKA time period – to follow up with patients regarding their progress with components of the PAS intervention. Because this intervention includes only 4 contacts, we have not defined a separate "minimum-acceptable" participation in the intervention. Ideal participation includes participation in all visits. As part of this exploratory trial, we will be monitoring the feasibility and rates of visit completion, in preparation for a larger trial. In this study, primary analyses will include all randomized participants, regardless of amount of intervention completion. However, we may conduct additional exploratory analyses that account for different patterns of intervention completion.

4.4 END-OF-STUDY DEFINITION

A participant is considered to have completed the study if he or she has completed 6-month follow-up assessment. As noted above, there is no minimum number of intervention visits required to meet at definition of "completion," but patterns of intervention completion will be assessed.

5 STUDY POPULATION

5.1 INCLUSION CRITERIA

All participants must be receiving post-TKA PT from a physical therapist at a UNC Healthcare System clinic or at physical therapy clinics outside of UNC. We will include individuals with OA in other lower extremity joints to maximize generalizability and help inform the larger trial.

5.2 EXCLUSION CRITERIA

Exclusion criteria are: significant cognitive impairment, neurological disorders affecting gait, systemic rheumatic disease; hospitalization for a cardiovascular condition the past six months; psychosis; substance abuse disorder; lower extremity surgery in the past year; planning total joint replacement in next 6 months; any other health conditions determined to be contraindications to a home exercise program.

5.3 LIFESTYLE CONSIDERATIONS

N/A

5.4 SCREEN FAILURES

Screen failures are defined as participants who consent to participate in this study but are not subsequently assigned to the study intervention or entered in the study. Individuals who do not meet the criteria for participation in this trial (screen failure) because of meeting one or more exclusion criteria (e.g., development of an exclusionary health condition) will not be rescreened. This is because of the brief period of time in which participants are eligible to participate in the study (e.g., time between initial screening and beginning of the intervention, which starts at the end of routine post-TKA PT). It is unlikely that any exclusionary health conditions, resulting in screen failure, will resolve during that period of time.

5.5. STRATEGIES FOR RECRUITMENT AND RETENTION

For UNC Healthcare clinics, we will identify potential participants though regular medical record searches of patients initiating outpatient post-TKA PT. About 10 patients initiate post-TKA PT at our target clinics monthly. Although we expect this will be sufficient to meet our sample size goal, we also have existing partnerships with and processes for working with other local PT clinics ³⁷. Potentially eligible patients will be mailed a recruitment letter (including an opt-out telephone number) from the study team, followed by a telephone call about 1 week later from a study team member to assess eligibility and interest. A UNC provider (physical therapist or orthopedic surgeon) may also discuss the study with a patient and will notify a study team member, if the patient agrees to be contacted. For non UNC Healthcare physical therapy clinics, staff will provide verbal information and / or recruitment flyers to participants regarding the study. With patients' verbal permission, a clinic team member may provide our UNC study team with contact information (telephone number, address) for the patient, so that we may contact them about the study. Patients may also directly contact the UNC study team, using the phone number provided on the flyer. Interest and eligibility of these patients will also be assessed via telephone.

Eligible patients will be asked to meet with a study team member to complete a baseline visit including informed consent, Health Insurance Portability and Accountability Act of 1996 (HIPAA) authorization and baseline assessments. We may review the informed consent and HIPAA over the phone prior to the baseline visit. At the end of the baseline visit, participants will be given an accelerometer to wear for one week and return via mail. Following receipt of the accelerometer, participants will be called by an un-blinded study team member with their randomization assignment, and the treating therapist will be notified accordingly.

6.0 STUDY INTERVENTIONS

6.1 STUDY INTERVENTION ADMINISTRATION

PAS Intervention Administration

Overview. Traditional post-TKA PT focuses on reducing pain and swelling and increasing range of motion (ROM) and strength. The PAS program significantly augments usual post-TKA PT, specifically addressing critical gaps of physical inactivity and joint loading asymmetry. The PAS program will be initiated during the final usual care PT visits, allowing integration and capitalizing on the existing patient-provider relationship. This is strategic timing because patients typically make substantial progress in traditional metrics (strength, ROM, pain) by this time point and are embarking on the independent phase of the recovery process. We will aim for PAS content to be included within the last two routine PT visits and will orchestrate this timing with study physical therapists. The course of PT may end slightly sooner or later than expected, and this exploratory study will allow us to fine tune processes for beginning delivery of PAS. PAS participants will then receive a follow-up call after 4 weeks (to assist with activity progression and problem-solving) and an additional visit (conducted in-person if possible or remotely via an IRB approved video platform or by phone if needed) after 8 weeks (to visually monitor exercise performance and re-assess proportional weight-bearing ability). Each of the contacts for the PAS intervention is summarized in Table 1 and described below. Participants will be asked to track performance of specific exercises and overall PA through Physiotec, a web-based tracking page. Physical therapists will have access to these pages to facilitate accountability and intervention delivery. If participants prefer not to log their exercise using Physiotec the study team will offer paper logs that can be used instead. In these cases, participants will be reminded to bring in their exercise logs for in-person sessions, and physical therapists will ask participants to refer to their logs during the 4-week phone call. For participants who do not have regular

Table 1. Overview of PAS Intervention Session Content				
	Balance Exercise (Loading Tota			
Session #	PA Counseling Content	Symmetry) Content	Minutes	
1 (In-Person or via video platform or phone if needed))	Overview of PA post-TKA, goal- setting, MI		15-20	
2 (In-Person, or via video platform or phone if needed)	+	50% weight-bearing exercise, assign home exercises	20-25	
3 (Phone) 4-weeks	Assess PA, address barriers, goal-setting, MI, community resources	Assess progress with exercises, advise on progression	25	
4 (In-Person, or via video platform or phone if needed) 8-Weeks	Assess PA, dealing with setbacks, MI long-term goal setting	Demonstration of exercises, advise on progression	40	

internet access (expected 9-10%) ³⁷, we will provide an iPad and data plan for the intervention period. Physical therapists will also track information from PAS sessions through a study clinic note template in the participant's medical record.

PAS Content: Counseling to Increase General Physical Activity
Specific content will be as follows:
Session 1 (In-Person if possible, or via video platform or phone if needed):
The PT will: (1) Emphasize the importance of PA in TKA recovery using key points. (2) Work with participants to establish a SMART

(Specific, Measurable, Attainable, Relevant, Time-bound) goal regarding overall PA. (3) Incorporate MI principles to elicit motivations and / or ambivalence toward PA ⁶⁹⁻⁷¹. (4) Provide a list of community-based and other resources to support overall PA. These materials will be emailed to the participant if the visit is conducted remotely.

Session 3 (4-Week Phone Session): The PT will: (1) Assess progress with overall PA using standard questions, referring to the web-based PA log. (2) Help participants to develop strategies to address any barriers they experienced in their PA. (3) Apply MI principles to elicit motivations and / or ambivalence toward PA. (4) Work with participants to establish a new SMART PA goal for the next four weeks, with appropriate progression. (5) Discuss PA resources and facilitate connection of participants to these resources.

Improving Physical Activity and Gait Symmetry after Total Knee Arthroplasty Protocol #19-0568

Version 11.0 6 October 2022

Session 4 (8-Week Session In-Person if possible or remotely via an IRB approved video platform or by phone if needed): Activities will mirror those for Session 3 with two modifications. First, the physical therapist will discuss strategies for dealing with setbacks in PA. Second, SMART goal setting will be more long term in nature, focusing on the next six months.

PAS Content: Balance Exercises to Improve Joint Loading Symmetry.

Although usual post-TKA PT aims to improve overall function, the PAS intervention differs substantially in its targeted approach to help patients detect side-to-side joint loading asymmetries and re-learn how to equalize loads across limbs. The content for this component of PAS will be as follows:

Session 2 (Second Session In-Person if possible, remotely via an IRB approved video platform or by phone if needed): If session is conducted in person, participants will undergo a process enabling them to detect when 50% weight bearing is achieved on each leg. The foot of the post-surgical limb will be placed on an analog bathroom scale and the contralateral foot on a small step of equivalent height. The participant will then shift weight between legs so that it feels as if 50% of weight is on each foot. The therapist will inform the participant of the actual weight distribution and assist the participant with achieving 50% weight bearing stance through verbal and tactile cues. The participant will then perform a series of 10 weight shifts off of the post-surgical limb and attempt to return to 50% weight bearing for a 10 second hold in that position. Participants who cannot successfully assume equal weight bearing within 5% for 8 of 10 trials will be given a scale and a step of equal height to continue practice at home by performing 10 repetitions of the weight shifting activity daily.

Table 2. PAS Intervention Balance and Functional Strength Exercises						
STATIC BALANCE	STATIC BALANCE DYNAMIC BALANCE*					
Initial Exercise: most challenging position that can be held for 3 repetitions, 10 seconds Initial Exercise: most challenging activity that can be performed for 10 consecutive repetitions without a loss of balance						
Progression Criterion: hold for 30 seconds, 3 repetitions	Progression Criterion: per repetitions without a loss of					
Exercis	ses (in order of difficulty)					
Staggered stance	Weight shift in staggered stance	Forward lunge to 45 degrees knee flexion and return				
Narrow staggered stance	Weight shift in tandem stance	Walking forward lunge				
Tandem stance	Tandem walk with arms outstretched	March with single leg hold for 3 seconds				
Single leg stance Tandem walk with arms crossed over chest Walking forward lunge with 3 seconds hold during transition						
*Physical therapist will assign 1 exe	ercise from each column.	·				

Next, the PT will prescribe balance exercises – one static and two dynamic (see Intervention Documents) - which supplement the general strengthening exercises assigned as part of usual post-TKA PT. The initial balance exercises prescribed will be the highest level at which the participant can perform at a minimal standard (defined in Table 2). If the visit is conducted remotely, the PT will be instructed to begin with the lowest level of balance exercises and to increase the level once they meet the progression criterion shown in Table 2. Participants will be given or emailed handouts and access to a website that displays proper exercise form. Participants will be instructed to perform exercises once daily. Static balance

exercises will be performed bilaterally in an alternating leg manner for three repetitions, 30-seconds each, with use of hand support as needed to maintain balance. *Dynamic balance exercises* will be performed bilaterally for 10 repetitions per set for three sets, with use of hand support as needed.

Session 3 (4-Week Telephone Session): The PT and participant will discuss recent performance of balance exercises (e.g, frequency, progression, problems with specific exercises) using standard questions (see Intervention Documents). This will ensure exercise performance is of appropriate intensity and frequency to achieve improvement. The therapist will encourage the participant to advance to the next level of an exercise has become too easy, based on criteria in Table 2.

Session 4 (8-Week Session In-Person if possible or remotely via an IRB approved video platform or by phone if needed): The PT and participant will discuss performance of balance exercises using standard questions (see Intervention Documents). Participants will demonstrate current exercises if the session is conducted in person or via video platform, and the therapist will correct form as needed. Progression of exercises will be promoted as described above. If session is delivered in-person, the therapist will also reassess participants' abilities to stand with equal weight bearing as described above in Session 2.

ATT Control Intervention Administration. The ATT control group will receive usual in-person post-TKA care, without the additional PAS components described for Sessions 1 and 2 in Table 1. To account for non-specific effects (e.g. therapists "attention") of the two additional visits in the PAS intervention (4-week phone call and 8-week visit), the ATT control group will receive visits at the same intervals but differing in content. Specifically, the 4-week phone call will include: information on typical recovery benchmarks for this time point, assessment of participants' daily activities, and reminders about symptoms that should trigger contacting a medical professional. The 8-week visit (conducted in-person if possible or remotely via an IRB approved video platform or by phone) will be primarily evaluative, including assessment of ROM, strength, and function when possible. If the visit is delivered via video, performance tests will be conducted, when feasible. Participants will be given or emailed a report summarizing these assessments. Participants will also be instructed to continue the home exercise program prescribed by their PT at discharge. This information may be delivered whether the visit is conducted in-person, via video or by phone. Neither of these contacts will include PA counseling or promotion of symmetrical loading of lower extremities, which are key components of the PAS intervention.

6.2 FIDELITY

Physical therapists will be trained by Drs. [name] (PA counseling) and [name] (balance exercises) and will conduct mock sessions of all PAS visits prior to study initiation. The study team and physical therapists will establish a formal description of usual care PT components, to help ensure the in-person ATT visits are distinct from the PAS visits. Study physical therapists will also be trained in delivery of the 4- and 8-week ATT control sessions. Since contamination between interventions is a challenge of this study design, we will aim to conduct monitoring of 75% of PT sessions to evaluate fidelity and the feasibility of using this approach for a larger trial.

6.3 MEASURES TO MINIMIZE BIAS: RANDOMIZATION AND BLINDING

The randomization scheme will be generated by the study statistician and stored within the study database. The database will be configured so that blinded study personnel (e.g., those conducting follow-up assessments) will not have access to randomization information. The participants will not be notified of randomization assignment until all baseline assessments are complete. In addition an individual participant's randomization assignment will not be known to any study personnel until baseline assessments are complete. Randomization will be stratified according to gender and presence of self-reported pain (≥3 on a 10 point scale) in any lower extremity joint (hip, knee or ankle) in addition to the surgical knee, to ensure that the groups are balanced in these respects.

6.4 STUDY INTERVENTION ADHERENCE

The study database will be used to track participants' completion of all assessment visits, as well as all intervention visits. Intervention visits will be logged in the UNC electronic medical record (EMR), and the study coordinator or other unblinded study team member will monitor these records for study participants to determine intervention adherence (and document the information in the study database). The study team will also maintain close communication with study physical therapists. If participants miss intervention visits, an unblinded study team member may assist the study physical therapist in contacting and rescheduling visits, as needed.

6.5 CONCOMITANT THERAPY

Participants will be permitted to continue any other post-TKA treatment (e.g., pain medications) during the course of the study.

7 STUDY INTERVENTION/ DISCONTINUATION AND PARTICIPANT DISCONTINUATION/WITHDRAWAL

7.1 DISCONTINUATION OF STUDY INTERVENTION

When a participant discontinues from the PAS intervention but not from the study, remaining study procedures will be completed as indicated by the study protocol. If a clinically significant finding is identified (including, but not limited to changes from baseline) after enrollment, the investigator or qualified designee will determine if any change in participant management is needed; the treating study physical therapist may be involved with these recommendations. Any new clinically relevant finding will be reported as an adverse event (AE). The data to be collected at the time of study intervention discontinuation will include the reason(s) for discontinuing the participant from the intervention, and methods for determining the need to discontinue.

7.2 PARTICIPANT DISCONTINUATION/WITHDRAWAL FROM THE STUDY

Participants are free to withdraw from participation in the study at any time upon request. An investigator may discontinue a participant from the study for the following reasons:

- Lost-to-follow up; unable to contact subject
- Any event or medical condition or situation occurs such that continued collection of follow-up study data would not be in the best interest of the participant or might require an additional treatment that would confound the interpretation of the study
- The participant meets an exclusion criterion (either newly developed or not previously recognized) that precludes further study participation

The reason for participant discontinuation or withdrawal from the study will be recorded in the study database. Participants who discontinue or are withdrawn will be replaced up to the point of randomization assignment being given to the participant. Once participants are given their randomization assignment, they will be counted toward the total study sample size and not replaced.

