9.3 POPULATIONS FOR ANALYSES

The primary analyses will be conducted using an intent-to-treat approach. Supportive exploratory analyses may be conducted to consider samples with greater completion of study intervention visits. Since this is a preliminary, exploratory analysis, the nature of these supportive analyses will be based on observed patterns of intervention visits. However, likely approach is to assess outcomes among participants who completed at least 3 of the 4 study visits.

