An additional advantage to using the GLMM approach is its ability to accommodate missing data (including dropouts, missed visits, and lost-to-follow-up) under a missing at random paradigm. All available follow-up data will be utilized in an intent-to-treat manner. If a participant is missing one of the follow-up time points, that participant is not completely excluded from the analysis. A supportive analysis will be conducted using multiple imputation to produce multiple datasets that have complete data for all n=60 participants, where missing values (due to dropouts, missed visits, and lost-to-follow-up) have been imputed. The statistical models will be fitted to each of the complete datasets; results of each model will be synthesized in a manner that accounts for both between and within imputation variation to produce final estimates to address the research questions.

Feasibility metrics will be computed as proportions, along with 95% confidence intervals to describe the level of uncertainty of the estimates. Lower confidence bounds of these proportions will be useful in considering worst-case scenarios when planning the subsequent large-scale trial. Acceptability data are primarily open-ended questions, and responses will be summarized to inform appropriate modifications to the PAS intervention. For the brief questionnaires on acceptability, appropriateness, and feasibility ^{95,96}, we will calculate mean and median scores and distributions across each domain.

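### Section 7.2 lets an investigator end outcome follow-up after randomization for a confounding treatment or a newly met exclusion criterion, which undermines the intent-to-treat analysis

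*Protocol*

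**What the plan says.** Protocol section 7.2 lists reasons for which an investigator may discontinue a participant from the study. Two matter here. One is an event or condition that "might require an additional treatment that would confound the interpretation of the study". The other reads "The participant meets an exclusion criterion (either newly developed or not previously recognized) that precludes further study participation".

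The rule operates after randomization. The same section says "Once participants are given their randomization assignment, they will be counted toward the total study sample size and not replaced". It also requires the reason for withdrawal to be recorded.

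Section 7.1 covers a different case: when a participant "discontinues from the PAS intervention but not from the study, remaining study procedures will be completed". No equivalent sentence covers someone discontinued under 7.2.

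On analysis, section 9.3 says "The primary analyses will be conducted using an intent-to-treat approach", and section 4.3 says that "primary analyses will include all randomized participants, regardless of amount of intervention completion". Section 9.4, repeated in the SAP, adds "All available follow-up data will be utilized in an intent-to-treat manner". It credits the mixed model with "its ability to accommodate missing data (including dropouts, missed visits, and lost-to-follow-up) under a missing at random paradigm" and plans multiple imputation for all 60 participants as support.

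**The concern.** Under intent-to-treat, a treatment received after randomization is part of the participant's course. That it might confound interpretation is not a reason to stop measuring the outcome. Section 7.2 makes it one.

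The exclusion criteria in section 5.2 include planned joint replacement, lower extremity surgery and hospitalization for a cardiovascular condition. Each could plausibly change MVPA or limb loading. Section 8.1 goes further: it collects injuries and progress toward TKA in the non-surgical limb as study data, so an event the trial sets out to record could also end follow-up.

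If such withdrawals differ between arms in number or in outcome, both co-primary contrasts can be biased. Section 9.4 says these contrasts will inform the sample size of the next trial, so the bias would carry forward. The protocol also leaves unclear which treatments count as confounding: section 6.5 lets participants continue other post-TKA treatment, while 7.2 allows withdrawal over an additional one.

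**Working it through.** **Plan's own figures.** Enrolment: 54/(1 - 0.10) = 60, as stated. Power of a two-sample t-test with 27 per group at two-sided 0.05, for 0.5 to 1.0 SD: 0.438, 0.581, 0.714, 0.822, 0.901, 0.950. These match the SAP table. At an assumed 80% power, 0.35 and 0.40 SD need 129 and 99 per group, consistent with the 100-130 in section 9.2. None of these figures is in dispute; they supply the 30 per arm and the 0.35-0.40 SD used below.

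**What the analysis conditions on.** The MVPA model has group, time, group-by-time and baseline MVPA, with a PAS-by-baseline term dropped if non-significant. The symmetry model adds walking speed. Triggering events and withdrawal reasons appear in neither. Someone withdrawn before the first follow-up contributes no response to the mixed model. Someone withdrawn later contributes the first follow-up only. The imputation model is not specified beyond covering all 60 participants, and no analysis departs from missing at random.

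**Illustrative size.** The documents give no withdrawal rate and no outcome gap, so both are assumed. Let k of the 30 in one arm be withdrawn, with outcomes averaging g SD below the full arm mean μ. The retained mean r satisfies

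30μ = k(μ - g) + (30 - k)r, so r - μ = g × k/(30 - k).

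| k withdrawn | g = 0.5 SD | g = 1.0 SD | g = 1.5 SD |
|---|---|---|---|
| 1 | 0.02 | 1/29 = 0.03 | 0.05 |
| 2 | 0.04 | 2/28 = 0.07 | 0.11 |
| 3 | 0.06 | 3/27 = 0.11 | 0.17 |

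At k = 3 and g = 1: 0.111/0.40 = 28% and 0.111/0.35 = 32% of the planning effect. Where a higher score is better, losses in PAS overstate its benefit and losses in the control arm understate it. With withdrawals in both arms the bias is the difference between the two shifts, and is zero when k and g are equal.

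**Error rate.** A simulation used no true effect, 30 per arm, k = 3 in one arm, a t-test at a single time point and 20,000 replicates, with the gap measured from retained participants instead of the full arm mean. Type I error was 0.051, 0.069 and 0.085 for gaps of 0.5, 1.0 and 1.5 SD. Neither calculation uses the planned mixed model, which could recover part of the shift through baseline and first follow-up values.

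**The case against.** A reader might infer that section 7.2 breaks intent-to-treat by deleting outcomes. It does not. Withdrawn participants stay in the randomized count, data already collected are used, someone missing one time point stays in the model, and all 60 are imputed. The rule stops future collection only.

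A reader might also infer that any newly met exclusion criterion forces removal. The wording is permissive, and this ground is limited to criteria that preclude further participation. In some of those cases follow-up may be unobtainable anyway.

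Nor do the documents show that those withdrawn would do worse, or that the person deciding knows the arm. Blinding of that decision is simply not stated. Missing at random could still hold given baseline and 3-month values.

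The most obvious trigger has been reduced. Planning joint replacement within 6 months is now an exclusion, and the amendment history says it was added to avoid such withdrawals. That screens plans at entry only. A plan formed later remains possible, and the schedule in section 1.3 counts 6 months from Visit 2, which follows screening.

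Finally, the standard error of the contrast at 27 per arm is √(2/27) = 0.27 SD, so shifts of 0.03 to 0.11 SD sit well inside sampling noise. That is fair for any test in this pilot. It is less reassuring for an estimate passed to a larger trial, because noise is reported in a confidence interval and this bias is not.

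These points limit the wording of the concern and its likely size. They do not explain why outcome collection should stop because a treatment confounds interpretation.

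**Conclusion.** The concern stands as a foreseeable and avoidable source of informative missingness, written into the protocol as a rule. It undermines the intent-to-treat analysis without breaking it, and no bias has been demonstrated.

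The 0.03 to 0.11 SD shift for one to three losses is an illustration. It rests on all losses falling in one arm and a 1 SD gap from the full arm mean. Matching losses and gaps would give zero.

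A reader might also conclude that the retention estimate for Aim 3 is distorted. The documents do not support that: reasons are recorded and completion is reported by arm, so investigator withdrawals can be separated from participant dropout. The plan only needs to say that they will be.

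**What to change.** In section 7.2:

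- Delete the confounding-treatment ground as a reason to end outcome collection.
- State that a newly met exclusion criterion does not by itself end outcome collection.
- Continue the 3- and 6-month assessments unless the participant withdraws or further data collection is not in the participant's best interest.
- Where a visit is not possible, use the telephone questionnaires and mailed accelerometer already allowed in section 8.1. The accelerometer recovers MVPA. Load symmetry needs the 10 m insole walk and stays missing.

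In section 9.4 and the SAP, say that the event is recorded, that data collected after it are analysed as randomized, and that investigator withdrawals are reported separately in the retention metric.

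Sections 6.5, 7.1 and 7.2 must be reconciled on additional treatment and on who stays in follow-up. This change concerns outcome collection only; any decision on continuing the intervention stays with the clinical team.

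The cost is a wording change and a few follow-up assessments that would otherwise have been dropped.
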